### 10.11 Laboratory Assessments

Laboratory results marked as clinically significant will be categorised as, “Abnormal, CS” and results marked as not clinically significant will be categorised as, “Abnormal, NCS”. Results within normal range will be marked as “Normal”. Not done results will be categorised as, “Not Done”.

### 10.12 Baseline

All analysis datasets containing measurements taken at more than one visit/time point will have baseline flags.

#### 10.12.1 Safety Endpoints

For safety endpoints, measurement taken at Visit 2 will be considered as baseline for both study periods.

#### 10.12.2 Efficacy Endpoints

Baseline will be derived for efficacy endpoints within each study period:

In both study periods, for NRS Pain Score and 11 point Likert scale for Symptoms (Nausea, Photophobia and Phonophobia) scores, ‘Pre-dose’ measurement will be considered as baseline.

Patients who reported migraine with missing pre-dose result for NRS or symptom scores will be flagged and discussed during blinded review meeting to define the baseline measurement.

### 10.13 Change from Baseline

Change between Baseline and post-baseline result will be calculated for all efficacy and safety endpoints within each study period as below:

- $\text{Change} = (\text{Result at Period X, Timepoint Y}) - (\text{Period X, Baseline Result})$

### 10.14 Extent of Exposure

The following parameters will be derived within each study period for exposure summaries:

Total dose administered (mg) = number of capsules consumed by the subject \* dose level consumed in mg

Number of capsules consumed will be determined by number of capsules returned at Visit 3 or Visit 4. Each bottle contains 2 capsules, and number of capsules returned will be subtracted to confirm the number of capsules consumed.

### 10.15 Analysis Flags

#### 10.15.1 Difference between Treatments

For subjects who took IMP in both visits, difference between their scores at each timepoint will be calculated as below.

Difference at timepoint X = Score (LAT8881 60 mg) at Timepoint X – Score (Placebo) at timepoint X.

### 10.15.2 Sustained Pain-Free

Subjects having no use of rescue medication and no relapse of headache pain within 24 hours after administration of IMP in each period will be separately flagged as ‘Sustained Pain-free’ for analysis.

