10.4 Exploratory endpoints

1. The percentage of subjects who are "sustained pain-free," defined as having no migraine headache pain at 24 hours, with no use of rescue medication and no relapse of headache pain within 24 hours (24-hour sustained pain-free) after administration
2. The time to first pain-free timepoint following treatment with oral LAT8881 compared with placebo to 24 hours post dose, with no use of rescue medication
3. Supplemental analgesic medication use in the 24 hour post treatment period
4. Subject satisfaction with each treatment based on a 7-point Likert Scale, overall preference for Treatment 1 or Treatment 2, and historical comparison with usual treatment
5. Association between change in headache pain and symptom scores and selected subject baseline characteristics, including for example, migraine with/without aura, relationship to menstrual cycle

11. Study measurements

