### 7.4 Exploratory Endpoints

- 1. The percentage of subjects who are "sustained pain-free," defined as having no migraine headache pain at 24 hours, with no use of rescue medication and no relapse of headache pain within 24 hours (24-hour sustained pain-free) after administration*
- 2. The time to first pain-free timepoint following treatment with oral LAT8881 compared with placebo to 24 hours post dose, with no use of rescue medication*
- 3. Supplemental analgesic medication use in the 24 hour post treatment period*
- 4. Subject satisfaction with each treatment based on a 7-point Likert Scale, overall preference for Treatment 1 or Treatment 2, and historical comparison with usual treatment*

5. *Association between change in headache pain and symptom scores and selected subject baseline characteristics, including for example, migraine with/without aura, relationship to menstrual cycle*

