### 10.15.4 Responder

Subjects achieving no migraine headache pain at each time point in each study period will be separately flagged for analysis. Presence or absence of pain will be determined as follows:

- Absence: NRS Pain score 0 or 1 at the corresponding timepoint.
- Presence: NRS Pain score more than 1 at the corresponding timepoint.

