## 10.16 Paired Difference in Pain-Free Subjects

Difference between treatments (LAT8881 – Placebo) for No Headache Pain at each timepoint, Sustained Pain-Free at 24 hours and First Pain-Free Timepoint will be calculated as below for the percentage difference; the numerator represents the difference in the number of subjects.

	Placebo		Total
	Pain free	Pain	
LAT8881			
Pain free	a	b	a + b
Pain	c	d	c + d

Total	a + c	B + d	a + b + c + d
-------	-------	-------	---------------

$$\text{Pain free for placebo (\%)} = \frac{a + c}{a + b + c + d}$$

$$\text{Pain free for LAT8881 (\%)} = \frac{a + b}{a + b + c + d}$$

$$\text{Pain free (LAT8881 - Placebo) (\%)} = \frac{a + b}{a + c + b + d} - \frac{a + c}{a + b + c + d} = \frac{b - c}{a + b + c + d}$$

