### 11.8.3 Exploratory Analysis

#### 11.8.3.1 Sustained Pain-free at 24 Hours

Number and percentage of subjects who are “sustained pain-free” at 24 hours (as defined in section 10.15.1) will be summarised treatment overall. The paired difference in number of subjects sustained pain-free (LAT8881 – Placebo) will be calculated as mentioned in section 10.16.

The summary will be based on Per-Protocol population.

In DDP: Table 14.2.5

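### The SAP's sustained pain-free flag drops the no-pain-at-24-hours condition, so a subject who is never out of pain counts as a success if no rescue is taken

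*SAP*

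**What the plan says.** The endpoint is stated in full twice. Protocol 10.4 (item 1) has "having no migraine headache pain at 24 hours, with no use of rescue medication and no relapse of headache pain within 24 hours". SAP 7.4 (item 1) has "defined as having no migraine headache pain at 24 hours, with no use of rescue medication and no relapse of headache pain", again within 24 hours. Both therefore require three things: absence of pain at 24 hours, no rescue and no relapse.

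The variable to be analysed is built in SAP 10.15.2, which flags "Subjects having no use of rescue medication and no relapse of headache pain within 24 hours after administration of IMP in each period". That is two conditions. The section refers neither to 7.4 nor to 10.15.4, where the pain threshold is set: "Absence: NRS Pain score 0 or 1 at the corresponding timepoint", with any higher score counted as pain.

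Two later sections use the flag:

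- SAP 11.8.3.1 summarises sustained status "as defined in section 10.15.1) will be summarised treatment overall". Section 10.15.1 is a different derivation: for subjects dosed in both periods, the "difference between their scores at each timepoint will be calculated as below".
- SAP 10.16 puts sustained status into a paired two-by-two table of pain free against pain: "Sustained Pain-Free at 24 hours and First Pain-Free Timepoint will be calculated as below for the percentage difference". It gives no rule of its own for who is sustained pain-free.

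Neither document defines relapse.

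**The concern.** A condition of no relapse is met trivially by a subject who never had relief. Once the 24-hour condition is left out, nothing in 10.15.2 requires the subject to have been free of pain at any time. Rescue is allowed from 2 hours after dosing but is not compulsory, so a subject can stay in pain for 24 hours without it. The rule as written labels that subject sustained pain-free, although the subject is a plain treatment failure.

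At stake are the percentage reported for each treatment and the paired difference in SAP 10.16. If subjects with unbroken pain and no rescue are spread unevenly between treatments, the difference moves, and it could move either way.

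**Working it through.** The documents state no figure for this endpoint, so there is none to reproduce. The check is a comparison of the two rules over every possible pain pattern, followed by the arithmetic of the paired difference.

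**Inputs**

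| Input | Value | Source |
|---|---|---|
| Post-dose scores | 7 (0.5, 1, 1.5, 2, 4, 8, 24 h) | SAP 7.1 |
| Absence of pain | NRS 0 or 1 | SAP 10.15.4 |
| Rule as written | no rescue, no relapse | SAP 10.15.2 |
| Endpoint | the same, plus no pain at 24 h | SAP 7.4, Protocol 10.4 |
| Planned completers / enrolled | 20 / 26 | SAP 4.2 |
| Relapse | pain after an earlier pain-free score | assumed; not defined in the documents |
| Diary | all scores present | assumed |

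**Step 1: patterns accepted.** Seven scores, each pain or no pain, give 2^7 = 128 patterns. Allowing rescue yes or no gives 256 profiles. The 128 with rescue fail both rules, so only the 128 without rescue matter.

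No relapse means that once a subject is pain-free, every later score is pain-free. A pattern is then fixed by where the first pain-free score falls:

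- first pain-free score at any of the 7 timepoints: 7 patterns, all pain-free at 24 h;
- no pain-free score at all: 1 pattern, in pain at 24 h.

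The rule in 10.15.2 accepts 7 + 1 = 8. The endpoint in 7.4 accepts 7. The only difference is pain at all seven scores. For example, a constant NRS of 7 without rescue is a success under 10.15.2 and a failure under 7.4.

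**Step 2: dependence on the meaning of relapse.** Suppose instead that relapse meant only return of pain after being pain-free at 2 h (assumed).

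- Pain at 2 h: 2^6 = 64 patterns, none of which can relapse.
- Pain-free at 2 h: the three later scores must be pain-free and the three earlier ones are free, so 2^3 = 8 patterns.
- Rule as written: 64 + 8 = 72. Endpoint: half of the 64 are pain-free at 24 h, so 32 + 8 = 40.

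The gap is then 72 against 40, wider than 8 against 7.

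**Step 3: effect on the reported figures.** One misflagged subject adds 1/20 = 5.0 points to a treatment's percentage, or 1/26 = 3.8 points if all 26 enrolled subjects were in the denominator.

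In SAP 10.16 the paired difference is (b − c)/N = [(a + b) − (a + c)]/N. Let uL and uP be the numbers with unbroken pain and no rescue on LAT8881 and placebo. The counts become a + b + uL and a + c + uP, so

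shift = (uL − uP)/N.

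For uL and uP between 0 and 3 (assumed) and N = 20, the limits are (0 − 3)/20 = −15 points and (3 − 0)/20 = +15 points. The shift is zero whenever uL = uP.

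**Step 4: illustration.** All counts are assumed, with N = 20.

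| Case | LAT8881 | Placebo | Difference |
|---|---|---|---|
| Endpoint as in 7.4 | 8/20 | 5/20 | 15 points |
| uL = 1, uP = 3 | 9/20 | 8/20 | 5 points |
| uL = 3, uP = 1 | 11/20 | 6/20 | 25 points |

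**The case against.** The best defence is that SAP 7.4 already holds the full definition and 10.15.2 is shorthand for it. The name of the flag, the heading of 11.8.3.1 and the pain-free and pain rows in 10.16 all point the same way, and a programmer who puts a constant NRS of 7 in the pain-free row has ignored all of them. This stands as evidence of intent: the endpoint itself has not been changed. It does not cure the derivation. None of those labels states the missing condition, and the section that should lead the reader to the rule cites the wrong one. The SAP is left with two rules for one variable.

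It is also fair to say that the effect size rests on assumption. Counting patterns does not show how often they occur, the −15 and +15 limits are extreme cases, and equal numbers on both treatments leave the paired difference unchanged. All of that stands, and the figures above show only what is possible.

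Finally, the endpoint is exploratory and descriptive. Pain scores and rescue use are listed by subject, so a wrong flag could be found and corrected without new data. That limits the importance of the point but does not make the written rule correct.

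**Conclusion.** The concern holds. As written, SAP 10.15.2 omits a condition that SAP 7.4 and Protocol 10.4 require, and it counts a subject with unbroken pain and no rescue as sustained pain-free. With complete scores and the ordinary meaning of relapse, that is the only pattern wrongly accepted; a narrower meaning of relapse would let in more. Each such subject adds 5.0 points to a treatment's percentage at N = 20. The direction and size of the net effect on the treatment difference cannot be determined from the documents. The primary analysis is not touched, and no p-value is planned for this endpoint. The SAP should be corrected, but the conduct of the trial is not in question.

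**What to change.** Rewrite SAP 10.15.2 so that a subject is flagged in a period only if all three of these hold:

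1. the 24-hour pain score is NRS 0 or 1, as in 10.15.4;
2. no rescue medication was used in the 24 hours after IMP;
3. there was no relapse in those 24 hours, meaning no score above 1 after an earlier score of 0 or 1.

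Change the reference in 11.8.3.1 from 10.15.1 to 10.15.2.

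Item 1 and the reference restore what the SAP already intends. The wording of relapse in item 3 is a proposal. The sponsor may prefer another, but one should be written down before unblinding. The same edit should say how a missing 24-hour score is handled, since the present rule does not call for that score at all. Neither definition says when freedom from pain must begin, so a subject first pain-free at 24 hours still qualifies; that is a separate matter.

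The cost is small: edits to two SAP sections and one added condition in a derived variable, using scores already collected. The protocol endpoint does not change. Protocol 14.1 already requires changes to the SAP to be described and justified in the final report.

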### 10.15.3 Time Deviated from Scheduled Timepoints

Actual time difference from ‘Time IMP was taken’ to each of the timepoints will be calculated and discussed during blinded review meeting and any analysis flags may be created to exclude the same.

Time deviated (hours) = (Time the corresponding timepoint recorded - Time IMP was taken) / 60.

Time difference between pre-dose measurement and IMP dosing should not be more than 30 mins. This difference will also be highlighted in the blinded review meeting.

### 10.15.4 Responder

Subjects achieving no migraine headache pain at each time point in each study period will be separately flagged for analysis. Presence or absence of pain will be determined as follows:

- Absence: NRS Pain score 0 or 1 at the corresponding timepoint.
- Presence: NRS Pain score more than 1 at the corresponding timepoint.

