4.2 Secondary objectives

1. To evaluate the effect of oral LAT8881 on migraine-associated symptoms compared with placebo, when assessed by the change in symptoms based on a 11- point Likert scale
2. To investigate the percentage of subjects achieving “no headache pain” following treatment with oral LAT8881 compared with placebo at any timepoint to 8 hours post dose, with no use of rescue medication
3. To evaluate the safety and tolerability of single doses of oral LAT8881 in subjects with migraine headache

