5.1 Overall study design

This is a randomised, placebo-controlled, double-blind, crossover, Phase IIa study to investigate the efficacy and safety of oral LAT8881 in acute migraine headache with or without aura. The overall study design is shown in

Figure 3. Details of the procedures during each phase are described in Section 9.

[figure not shown]

Figure 3: Overall study design for LAT-MIG-001

Subjects entered into the study will be randomised to receive IMP (LAT8881 60 mg or placebo), to be taken at the onset (within one hour from the onset of pain) of a migraine headache of moderate to severe intensity. Rescue medication should not be taken until at least 2 hours post dose. Subjects will be given one dose of IMP (2 capsules), to treat one migraine headache.

After treatment of one migraine headache (or a maximum 28 days) the subject will return to the clinic for re-evaluation and crossover to the second treatment. In the second treatment period, they will take IMP in the same manner as in treatment period 1.

A followup (End of study) visit will occur within 7 days after treatment of one migraine headache in the second treatment period or a maximum 8 weeks from randomisation.

Subjects will complete diaries to record menstrual cycle (in menstruating females), onset and nature of migraine and non-migraine headaches, pain scores at time of IMP dosing and various time points post dose, associated symptoms and rescue medication. Adverse events will be monitored.

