8.2.3 Permitted medications

The following medications are permitted:

- 1 Rescue analgesics, 2 or more hours after dose of IMP: prescription and nonprescription drugs including Standard of Care medications for treatment of acute migraine headache
- 2 Other medications eg vitamins, herbal/dietary supplements (including Chinese medicines), oral and IUD contraceptives, hormone replacement therapy, not on the prohibited medications list which have been stable for 3 months prior to screening.

Subjects who change concomitant medication during the study period should notify the investigator promptly and details of the medications used should be documented in the source documents and CRF. Concomitant medications will be recorded by both the generic and the Trade name.

9. Study procedures

The Schedule of Assessments for the study are provided in Section 2.

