10.2 Secondary endpoints

1. Change in migraine-associated symptoms of nausea, photophobia and phonophobia. Symptoms are assessed on an 11- point Likert scale with 0 = no symptoms and 10 being severe symptoms at time of dosing and at 0.5, 1.0, 1.5, 2, 4, 8 and 24 hours post dose.
2. Change in each subject's most troublesome symptom that may include nausea, photophobia and phonophobia cognitive impairment, dizziness and functional disability. Symptoms are assessed on an 11- point Likert scale with 0 = no symptoms and 10 being severe symptoms at time of dosing and at 0.5, 1.0, 1.5, 2, 4, 8 and 24 hours post dose.
3. The percentage of subjects achieving "no headache pain" at 0.5, 1.0, 1.5, 2, 4 and 8 hours post dose

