14.5 Analysis of efficacy data

The primary population for analysis of efficacy data is the PP population. All summary tables and results of statistical analyses will be presented for the PP population for all efficacy endpoints. In addition, all

summary tables and results will be presented for the FAS population.

Individual pain score-time profiles for each treatment within each subject will be presented graphically. The difference between the NRS pain scores at each timepoint for LAT8881 60 mg compared with placebo within each subject will be estimated and presented graphically. The number of subjects, mean, standard deviation, minimum and maximum NRS pain score at each timepoint, change from baseline, difference between treatments at each timepoint and change from baseline difference between treatments will be presented for each treatment overall and within each treatment period.

Nausea, photophobia and phonophobia symptom scores will be summarised and presented in the same way as the pain scores. The number and percent of headaches with each most troublesome symptom of migraine including nausea, cognitive impairment, dizziness, functional disability, photophobia and phonophobia will be summarised for each treatment. The most troublesome symptom scores will be summarised and presented in the same way as the pain scores.

The number and percent of subjects with 'no headache pain' at each time point will be presented for each treatment. Two-way tables will present the presence/absence of pain classified for each treatment at each timepoint. Absence of pain will be defined as a pain NRS score of 0 or 1.

The number and percent of subjects who are "sustained pain-free" at 24 hours after dose of IMP will be presented by treatment. A two-way table will present the "sustained pain-free" status for subjects on each treatment.

The number and percent of subjects will be summarised by their first pain-free timepoint. A two-way table will present the classification of each subject's first pain-free timepoint by treatment. Kaplan-Meier curves will present the time to first pain-free timepoint.

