#### **11.8.2.5 No Headache Pain**

Number and percentage of subjects who achieve 'no headache pain' (NRS pain score 0 or 1) at each timepoint will be presented by treatment overall. Presence or absence of pain will be determined as

mentioned in section 10.15.4. The paired difference in number of subjects with no headache pain (LAT8881 – Placebo) will be calculated as mentioned in section 10.16.

In DDP: Table 14.2.4

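### Time to first pain-free, and the 4- and 8-hour pain-free percentages, count relief after rescue, although exploratory endpoint 2 and secondary objective 2 exclude it

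*SAP*

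**What the plan says.** Exploratory endpoint 2 (Protocol 10.4, SAP 7.4) is the time to the first pain-free timepoint, followed to 24 hours, on condition that no rescue is used. SAP 10.15.5 derives it from the first score of 0 or 1 and censors at 24 hours those who never reach one. It does not mention rescue.

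Secondary objective 2 (Protocol 4.2, repeated in SAP 3.2) asks for the percentage free of headache pain "compared with placebo at any timepoint to 8 hours post dose, with no use of rescue medication". The matching secondary endpoint 3 (Protocol 10.2, SAP 7.2) gives the assessment times, "at 0.5, 1.0, 1.5, 2, 4 and 8 hours post dose", and leaves the rescue condition out. Protocol 14.5 says "Absence of pain will be defined as a pain NRS score of 0 or 1". SAP 10.15.4 has "Absence: NRS Pain score 0 or 1 at the corresponding timepoint", and SAP 11.8.2.5 tabulates that flag.

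On rescue itself, Protocol 5.1 says "Rescue medication should not be taken until at least 2 hours post dose". Protocol 8.2.3 then permits "prescription and nonprescription drugs including Standard of Care medications for treatment of acute migraine headache".

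For one pain-free result the SAP does apply the condition. SAP 10.15.2 flags as sustained pain-free "Subjects having no use of rescue medication and no relapse of headache pain within 24 hours after administration of IMP in each period".

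**The concern.** A subject whose attack does not respond to study drug may take a standard migraine treatment after 2 hours and score 0 or 1 at 4 or 8 hours. As the rules stand, that subject is a responder on the randomised treatment at that timepoint, and has an event on the time-to-first-pain-free curve. Both results would then describe study drug plus whatever rescue was taken, which is not the question that the endpoint and the objective ask.

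The time-to-first-pain-free derivation is the clearer case, because it conflicts with the wording of its own endpoint. For the responder percentages the break lies higher up, between objective 2 and the endpoint and analysis text written to serve it.

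**Working it through.** **1. Question against rule**

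| Result | What is asked | What the rule counts |
|---|---|---|
| Time to first pain-free, to 24 h | No rescue (endpoint: Protocol 10.4, SAP 7.4) | First score 0 or 1, rescue ignored (SAP 10.15.5) |
| Pain-free percentage, to 8 h | No rescue (objective: Protocol 4.2, SAP 3.2); endpoint 3 silent | Score 0 or 1, rescue ignored (Protocol 14.5, SAP 10.15.4, 11.8.2.5) |
| Sustained pain-free, 24 h | No rescue (endpoint: Protocol 10.4, SAP 7.4) | No rescue (SAP 10.15.2) |

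**2. Does another rule repair it?** No.
- SAP 9.2 removes subjects from the per-protocol population for major deviations, and permitted rescue is not a deviation.
- SAP 8.2 defers only imputation for the primary endpoint.
- SAP 10.15.3 concerns late or early entries.
- SAP 10.16 takes the flags as given.
- SAP 8.1, on changes to planned analyses, does not mention dropping the condition.

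**3. Which timepoints?** Permitted rescue starts at 2 hours, so it reaches the 4- and 8-hour percentages and the curve up to 24 hours. Scores at 0.5 to 1.5 hours are affected only by rescue taken against protocol. The 2-hour score is affected only by such early rescue or by a late entry.

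**4. Size for each rate.** The documents give no pain-free or rescue rates, so every rate below is an assumption. The only planned figure used is 20 completers. The enrolment behind it holds up: 20/0.80 = 25 against the stated 26, and 26 × 0.80 = 20.8.

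Let p be the share scoring 0 or 1 without prior rescue, r the share of the rest who took rescue before the score, q the share of those who then score 0 or 1, and s = r × q.

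Reported rate = p + (1 − p)s. This is never below p.

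Assume p = 0.20 on placebo and 0.40 on LAT8881, r from 0.3 to 0.8 and q from 0.2 to 0.6. Then s runs from 0.3 × 0.2 = 0.06 to 0.8 × 0.6 = 0.48.
- Placebo: 0.20 + 0.80 × 0.06 = 24.8%, to 0.20 + 0.80 × 0.48 = 58.4%.
- LAT8881: 0.40 + 0.60 × 0.06 = 43.6%, to 0.40 + 0.60 × 0.48 = 68.8%.
- Extra responders among 20: placebo 16 × s = 0.96 to 7.68; LAT8881 12 × s = 0.72 to 5.76.

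**5. Size for the difference.** With P for placebo and T for LAT8881,

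reported difference = (p_T − p_P) − [(1 − p_P)s_P − (1 − p_T)s_T].

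It shrinks only if the bracket is positive. The true difference below is 20 points.

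| Assumed setting | Placebo | LAT8881 | Difference |
|---|---|---|---|
| Equal s = 0.06 | 24.8% | 43.6% | 18.8 |
| Equal s = 0.48 | 58.4% | 68.8% | 10.4 |
| r = 0.8 placebo, 0.6 LAT8881; q = 0.2 | 32.8% | 47.2% | 14.4 |
| Same r; q = 0.6 | 58.4% | 61.6% | 3.2 |
| Half of all subjects in each arm take rescue; q = 0.5 | 45% | 65% | 20 |
| r = 0.5 in both; q = 0.3 placebo, 0.6 LAT8881 | 32% | 58% | 26 |

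With equal s the bias is s times the true difference: 1.2 to 9.6 points here, but only 0.3 to 2.4 points if the true difference is 5. For scale, the standard error of a 20-pair difference, treating the periods as independent, is √[(0.4 × 0.6 + 0.2 × 0.8)/20] = √0.02 = 14.1 points.

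**The case against.** The SAP's responder flag is not a departure from the protocol's analysis. Secondary endpoint 3 omits the rescue condition and Protocol 14.5 defines absence of pain by score alone, so SAP 10.15.4 and 11.8.2.5 do what those sections say. That stands. A reader might infer that the SAP dropped a protocol rule here, but for the percentages the documents show only that the objective was not carried into the endpoint. The defence does not extend to SAP 10.15.5, whose endpoint states the condition.

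A reader might also infer that the gap biases the comparison against LAT8881. The documents do not support that as a fact. Shrinkage follows if the drug works, placebo non-responders use rescue at least as often, and post-rescue response is similar. The last two rows of the table show no change and an increase under other assumptions.

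The results are descriptive: counts, percentages, a paired difference and a Kaplan-Meier curve, with no test specified and no formal hypotheses. SAP 11.6 also tabulates concomitant medication by treatment, with rescue shown separately and first, so a reader would see unequal rescue use. Both facts limit the consequence. Neither links rescue to the flags, so the reported percentage and curve still answer a different question. The separate Data Display Plan is not available, so its table layouts could not be checked.

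**Conclusion.** The point holds, and it is minor. SAP 10.15.5 contradicts its own endpoint. SAP 10.15.4 and 11.8.2.5, in line with Protocol 14.5 and endpoint 3, produce percentages that do not answer secondary objective 2. The wording gap is certain. Relative to the rescue-free definition, reported pain-free rates can only be too high.

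How much too high is unknown. The working gives about 4 to 38 points on placebo (24.8 − 20 = 4.8; 58.4 − 20 = 38.4) and 4 to 29 on LAT8881 (43.6 − 40 = 3.6; 68.8 − 40 = 28.8), on assumed inputs; the upper ends need the top of both the rescue and post-rescue response ranges. No direction can be claimed for the treatment difference without rescue use and post-rescue response by arm. The affected results are secondary or exploratory, and the percentages at 0.5 to 2 hours are essentially untouched.

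**What to change.** Change the SAP only, before database lock:

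- **10.15.4 and 11.8.2.5:** count a timepoint as free of headache pain only if the score is 0 or 1 and no rescue was taken between that period's dose and that score. Scores before rescue keep their own result.
- **10.15.5:** do not count a score of 0 or 1 after rescue as an event. Censor that subject at 24 hours, as the SAP already does for subjects who never become pain-free.
- **Rescue timing:** take it from the migraine diary, which collects concomitant medication with the scores (Protocol 9.3), and from the concomitant medication data. Settle unclear order case by case at the existing blinded review. A blanket rule that fails every score from 4 hours would misclassify someone who was pain-free at 4 and 8 hours and took rescue for a later relapse.
- **Supportive row:** keep the score-only count beside the main one, and record the added condition in SAP 8.1.

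No protocol or diary amendment is needed, so no ethics committee step arises. The cost is one condition in the derivations, using data already collected. Reported pain-free rates will be somewhat lower, and a subject who takes rescue while already at 0 or 1 will count as not pain-free at later timepoints.
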